5.5.2 Intervention Allocation

The TCTU TRuST system will allocate patients randomised to the two groups and generate both an on-screen message at time of randomisation and an e-mail to the PI and CI.

5.5.3 Withdrawal procedures

Although a participant is not obliged to give reason(s) for withdrawing prematurely, if the participant appears lost to follow up, the Chief Investigator (CI) will make a reasonable effort to ascertain the reason(s), while fully respecting the individual's rights, and will demonstrate that everything possible was done in an attempt to find any participant lost to follow-up. Those lost to follow-up or withdrawn will be identified and a descriptive analysis of them provided, including the reasons for their loss and its relationship to treatment and outcome.

If participants withdraw/dropout within 3 months of treatment, no further records would be collected, as any change would not be clinically meaningful. Any data collected thus far will be imputed and intention to treat analysis will be used.

If participants withdraw/dropout after 3-month period, attempt to clinically measure overjet will be made and any previously collected questionnaire data, 3D facial scans, scans of teeth and questionnaire data will be imputed and intention to treat analysis will be used.

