However, like all removable functional appliances, compliance with the removable Twinblock appliance can be problematic. The issue with compliance has been quantified by Parekh et al (2019) for the Twinblock appliance at mean daily wear of 12.38 hours or 51.6% of that recommended. Furthermore, age is also a factor in compliance with O'Brien et al. (2003c) finding older patients had unusually high failure rates (34%) compared to younger patients (O'Brien et al. 2003a) at 19%. The solution to the problem of compliance is to use a fixed functional appliance. The oldest known fixed functional appliance is the Herbst appliance which was first described at the start of the 20th century and re-introduced by Hans Pancherz more recently. It is comprised of two maxillary and mandibular sections – either cast or banded. However, problems include breakages, regular re-cementing of the appliance, and patient acceptance. The most recent version of the Herbst appliance was used in the UK MRC-funded multicentre RCT (O'Brien et al. 2003c) comparing the removable Twinblock appliance with the Herbst. The rate of failure during the functional phase was surprisingly high in the Twinblock group at 34%, and much lower in the Herbst group at 13%.

Combining the extensive research literature on the Herbst appliance with clinical experience produces the following summary:

- The Herbst appliance reduces almost all overjets in 6 months which compares to an average of nine months with the removable Twinblock appliance
- Patients find the Herbst appliance not excessively intrusive after the first week like the removable Twinblock appliance
- There is an inconveniently high rate of decementation, mechanical failure and lower incisor proclination with the Herbst appliance
- A functional appliance that can be rapidly and reliably added to a conventional fixed appliance will probably prove very popular.

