The Bass Dynamax appliance has been proposed as an alternative and an improvement to the Herbst appliance. It is a two-part appliance, with the interlock lingual to the occlusal surfaces of the teeth. The lower half can be fixed or removable and this design has some of the attributes of other appliances. Whilst it has potential advantages including theoretical incremental advancement resulting in greater co-operation and potentially greater contribution of mandibular growth than dentoalveolar effects, it remains un-resolved whether the Bass Dynamax is more efficient than other functional appliances as a substantial UK RCT involving this appliance and a Twinblock appliances has been abandoned due to excessive breakages of the Dynamax (Thiruvenkatachari et al.2010). This appliance is therefore not used widely.

The fixed design of the Twinblock appliance has three significant advantages when compared to a Herbst and Dynamax appliances:

• The appliance is significantly cheaper as no complex components are required for construction whilst the clinician involvement in treatment is no more complicated when compared to other removable functional appliances

- The appliance is located on the occlusal plane and not in the buccal sulcus, which assists robustness and patient comfort
- Because the two halves of the appliance are not permanently linked together, the problems of leverage on the fixation points does not arise.

However, the simplicity and versatility of the fixed Twinblock appliance in relation to accelerating functional appliance treatment times remains to be tested. Initial data from a scoping study (REC 17/ES/0126) shows significant difference in overjet reduction at 3 months treatment duration with the fixed Twinblock. The patient experience with the Fixed Twinblock did not report any negative experience in relation to soreness from the appliance. Free text comments from patients were positive for the use of the fixed appliance.

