4.6 TRIAL SAFETY ASSESSMENTS

This is a low risk trial, and no serious adverse events are anticipated. However, it is possible that there may be allergic reactions to the Twinblocks and this will be recorded as an expected adverse event in the CRF. The Twinblock appliance treatment will be discontinued in case of allergic reaction and discontinued from the trial and other options for management of the increased overjet will be provided. The site PI will report any SAE that is both related to the research procedures and is unexpected to the CI and the CI will send an NRES Safety Report to the appropriate REC within 15 days of becoming aware of the event. A copy of the Report will be sent in parallel to the Sponsor. An annual progress report will be submitted to the appropriate REC and a copy of the Report will be sent in parallel to the Sponsor.

Consideration and potential impact of the trial following the peak of the COVID-19 pandemic have been mitigated to ensure safety of participants and staff. The visits for treatment during the trial will be part of routine non aerosol generating dental care, with physical access to the dental hospital/orthodontic practice complying with Scottish government restrictions on social distancing. This information will be provided to participant and parent/carer prior to attendance and suitably prepared ahead of their appointment so that total contact time spent in the dental hospital/ orthodontic practice is reduced. Covid-19 screening will be undertaken ahead of the visit where possible and a high level of hand hygiene will be adopted with the provision of antiseptic hand gel on entrance and exit. To reduce contamination, minimised wait times in common areas will be adopted and safe entry/exit will be ensured with appropriate signage. Face coverings will be required to be worn where indicated by Scottish government guidance.

Radiographs are part of routine clinical investigations. Effective Dose per lateral cephalogram - 0.004mSv (from HPA-CRCE-012 'Frequency and Collective Dose for Medical and Dental X-Ray Examinations in the UK, 2008'). As the patients in this study are 9-14 years old, the risk is age corrected to 11% per Sv. The combined risk of cancer mortality from both exposures in this study is of the order of 1 in 1.1 million

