8.3 MISSING DATA

Incomplete data will be imputed and intention to treat analysis will be used to include subjects who terminate the trial early (see 5.5.3 above)

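### Overjet is not measured again in participants who leave within 3 months, so for them the intention-to-treat estimate rests on imputing data the protocol chose not to collect

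*Protocol*

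**What the plan says.** Protocol section 5.5.3 sets two rules by time of leaving.

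- Within 3 months: "If participants withdraw/dropout within 3 months of treatment, no further records would be collected, as any change would not be clinically meaningful". It continues: "Any data collected thus far will be imputed and intention to treat analysis will be used".
- Later: "If participants withdraw/dropout after 3-month period, attempt to clinically measure overjet will be made", and earlier data are again to be imputed under intention to treat.

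Section 8.3 repeats the principle: "Incomplete data will be imputed and intention to treat analysis will be used to include subjects who terminate the trial early". Section 5.5.3 also promises a descriptive account of those lost, covering their reasons and how the loss relates to treatment and outcome.

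The primary outcome is overjet change in mm per month (sections 3.2.1 and 8.2). Table 1 lists T0 to T5 as its time points, and section 6.1 places T1 at 3 months. Section 2 says that scoping data "shows significant difference in overjet reduction at 3 months treatment duration with the fixed Twinblock". Section 4.6 says that the appliance treatment "will be discontinued in case of allergic reaction and discontinued from the trial". Nowhere does the protocol separate stopping the appliance from withdrawing consent to be followed up.

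**The concern.** The rule withholds measurement from one group of randomised participants because little will have happened to them. Little change is itself the outcome of an early failure. It is information about the treatment policy and no reason to leave the outcome unrecorded.

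The trial exists because wear of the removable appliance is unreliable. Section 2 says that patients who do not wear removable functional appliances gain nothing. It quotes functional-phase failure of 34% with the removable Twinblock against 13% with the Herbst, another fixed appliance. Stopping that depends on both arm and outcome is therefore plausible, and that is the situation in which imputation from baseline alone is least safe.

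The choice of imputation method may properly sit in a statistical analysis plan that is not shown. The decision not to collect the reading sits in the protocol, and no analysis plan can reverse it afterwards.

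**Working it through.** **1. The plan's own figure.** Section 8.1 gives a difference of 81 days and an SD of 101 days, so d = 81/101 = 0.80. A two-sided t-test (sidedness assumed) at 5% with 80% power needs 25.4 per arm, rounded up to 26, where power is 80.9%. Allowing 40% loss, 26/0.6 = 43.3, rounded up to 44 per arm and 88 in total. The stated sample size reproduces and is not at issue.

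**2. What an early leaver contributes.** After T0 the next scheduled overjet is T1 at 3 months. Someone who leaves before T1 has the baseline value and any reading taken at an interim appointment. Someone who leaves after T1 should have at least the T1 reading, and a further reading is attempted. The group with the least data is thus the one for which no more is sought.

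**3. The rationale against other parts of the protocol.**

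- T1 is a primary-outcome time point, and a difference at 3 months is cited as supporting evidence. The view that early change carries no meaning sits uneasily with both.
- The promised description of how loss relates to outcome cannot be given for people whose outcome is not recorded.
- Section 11.2 provides, if required, an end-of-trial assessment for participants who leave because of an adverse event. Section 5.5.3 makes no matching exception before 3 months.

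**4. Possible size.** Let early leavers make up a fraction p of an arm, with a mean outcome g SD worse than that arm's completers. The true arm mean is then (completer mean) − p × g. If leavers are imputed as completers, the imputed arm mean is the completer mean. The error in the fixed-minus-removable difference is

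error = (p_fixed − p_removable) × g.

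If the removable arm loses more, the advantage of the fixed appliance is understated; if the fixed arm loses more, it is overstated. Neither p nor g is in the protocol. I assume g from 0.5 to 1.5, the same in both arms, and take the planned 0.80 SD as the yardstick. That figure was set in days, so applying it to mm per month is also an assumption.

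| Gap in early loss | Absolute error, g = 0.5 | Absolute error, g = 1.5 | Share of 0.80 SD |
|---|---|---|---|
| 0 points | 0 | 0 | 0% |
| 10 points | 0.10 × 0.5 = 0.05 SD | 0.10 × 1.5 = 0.15 SD | 6% to 19% |
| 21 points (34% − 13%) | 0.21 × 0.5 = 0.105 SD | 0.21 × 1.5 = 0.315 SD | 13% to 39% |

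The last row is an upper illustration only. Those rates cover the whole functional phase, and the 13% belongs to a different fixed appliance. If half of that gap arose in the first 3 months, it would be 10.5 points, close to the middle row.

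**The case against.** The strongest reply is that the documents fix neither the direction nor the size of any bias. Early loss by arm is not given, the imputation method is open, and equal loss with equal imputation error gives no bias. Section 6.1 has overjet measured at all appointments, so some early leavers will have interim readings. Imputation could also borrow from later leavers, whose overjet is sought. Carrying the last value forward would be consistent with the stated rationale and would not treat failures as completers. All of this stands, and it is why the figures above are scenarios.

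Several stronger readings are tempting but not supported:

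- **That intention to treat is broken.** All randomised participants stay in the analysis through imputation. The weakness lies in what supports their values.
- **That the scoping result contradicts the rule.** That result is a significant difference at 3 months; the rule concerns people who stop before then. The rationale is in tension with it, no more.
- **That type I error is badly inflated.** This would need single imputation, with the full 40% allowance missing and analysed as if observed. The protocol does not specify single imputation, and section 8.1 applies the 40% to dropout or incomplete data over the whole of a long treatment.
- **That early stoppers are mostly treatment failures.** No early-dropout data are given.
- **That observed values will be overwritten.** The sentence on imputing data collected so far can be read that way, but loose drafting is the likelier explanation.

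**Conclusion.** The point holds in a limited form, and the rule should be fixed. The protocol stops collecting the primary outcome for early leavers, although it treats measurement after dropout as feasible for later ones. For early leavers the intention-to-treat estimate then rests on an imputation that cannot be tested.

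The bias may be zero. Under completer-like imputation, an assumed shortfall of 0.5 to 1.5 SD and a 10-point difference in early loss, it is about 0.05 to 0.15 SD, or 6% to 19% of the planned effect. The range of 0.11 to 0.32 SD from the 34% against 13% gap is a ceiling for illustration and should not be read as an expected value. The finding itself rests on the text of section 5.5.3 and does not depend on these figures.

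**What to change.** Amend section 5.5.3, and align sections 4.6 and 8.3 with it:

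1. Delete the 3-month exception and the rationale given for it.
2. Distinguish stopping the appliance from withdrawing consent to follow-up.
3. Unless that consent is withdrawn, attempt the overjet measurement at the scheduled time points for every randomised participant, whenever and for whatever reason the appliance was stopped, allergy included. Record any other overjet treatment received.
4. State that observed values are kept and not imputed over. Include all observed overjets in the multilevel model already planned in section 8.2.
5. Add one sensitivity analysis that assumes no further change after stopping.

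This changes data collection and analysis only. It leaves untouched the clinical rules on when an appliance is stopped and what care follows.

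The cost is amendment wording, some contact effort and a ruler reading. Nothing in the protocol shows that stoppers would keep attending, so some will still be missing. Later readings in those who move to other overjet management may partly reflect that treatment, which is why it should be recorded. The sample size does not change.

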6 DATA COLLECTION& MANAGEMENT

6.1 DATA COLLECTION

Overjet measurement

Overjet will be measured (in millimetres) between the upper incisal edge and the labial surface of the lower incisors using a metal ruler at all appointments to assess rate of reduction. This will be measured at start of treatment (T0), 3 months (T1), 6 months (T2), 9 months (T3), end of Twinblock appliance phase, i.e., when overjet has reduced to 0-3mm and remains unchanged at two consecutive appointments (T4), for a maximum of 12 months from start of treatment and end of fixed appliance treatment (T5). If overjet has reduced earlier than anticipated, follow-up time points will be skipped to T4 and T5.

Impressions

A negative imprint of teeth and soft tissues will be made using alginate impression material to produce plaster models (positive reproduction), allowing fabrication of the fixed and removable Twinblocks at the Orthodontics laboratory within Dundee Dental Hospital. A typical impression takes 10 minutes and is routine procedure for all patients undergoing Orthodontic treatment.

Intra oral scans

3Shape Trios® or iTero Element ® will be used to record intra- Oral scans for digital study models. These use a non-contact laser scanning technology to record a three-dimensional record of the tooth position and occlusion. A scan takes 10 minutes to collect depending on operator experience and patient compliance. There is no discomfort or sensation associated with the scanning procedure. The pre- and post-treatment study models are essential records in orthodontics and the digital version will allow precise tracking and quantifying (mapping) of tooth movements during treatment. The mapping of teeth movements will provide details of the extent of dental contributions in overjet reduction. If an intraoral scanner is not available at a site, the impression or plaster models will be scanned using the 3Shape dental lab 3D scanner. The superimposition function on 3Shape Ortho Analyzer software will be used to calculate distance between pre- and post-treatment scan landmarks in millimetres.

Stereophotogrammetry

Vectra® H1 handheld 3D camera will be used to record the patient's three-dimensional (3D) facial characteristics, allowing quantification of 3D soft tissue volume changes. The camera works like any other and would require three facial captures which are automatically stitched into one 3D image with the provided software. The whole process will take 10 minutes. The need for 3D quantification of the soft-tissue effects of functional appliances has been highlighted (Flores-Mir 2006). The immediate soft tissue effects, especially of the soft tissue chin (Sharma 2005) have been shown to be only 40% of the predicted outcome (Salloum 2018). Landmarking of the pre- and post-treatment 3D images will be done using the VAM (Vectra Analysis Module) software and superimposed to measure the difference in linear distance in millimetres.

Lateral Cephalogram

Cephalometric radiographs are routinely taken as part of assessment and planning for orthodontic treatment. Modern digital lateral cephalometric radiographs are very low dose. It is used to assess whether the aetiology of malocclusion is due to skeletal relationship, dental relationship or both and quantify treatment changes. The radiographs will be taken at baseline, end of twinblock treatment and towards end (near end) of fixed appliance treatment in accordance with normal clinical practice. Eastman cephalometric analysis (Mills, 1982) will be done on the radiographs to assess the skeletal and dental changes associated with both the groups. The analysis will include angles SNA (sells-nasion-point A), SNB (sella-nasion-point B), ANB (difference between SNA and SNB), upper incisor long axis to maxillary plane (anterior nasal spine -posterior nasal spine), lower incisor to mandibular plane (gonion-menton), MMPA (maxillary-mandibular plane) and linear measurements - facial proportion (ratio of lower face height to total anterior face height) and APog (tip of lower incisor form line connecting point A-Pogonion)

Patient Experience questionnaire

This validated questionnaire, based on the three-questionnaire approach, will evaluate patients perception of their malocclusion pretreatment (T0) and patients' experience with wearing the fixed and removable Twinblock appliances 3 months into treatment (T1) and at the end of Twinblock phase of treatment (T4).

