3.2 OUTCOMES

3.2.1 Primary Outcomes

1. Rate of overjet correction by comparing change in millimetre/month from clinical measurements with fixed and removable Twinblock appliances.

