7 CLINICAL PROTOCOL AND TRIAL PLAN

7.1 FIXED TWINBLOCK APPLIANCE DESIGN

The fixed Twinblock (*Figure 1*) comes as preformed occlusal blocks and wires. The occlusal blocks will be custom adapted to the individual participant's models with the upper block fitted to cover the second premolar and extend distally over the molars. The lower block will cover the premolars, avoiding the cusp of the canine.

In occlusion, the occlusal blocks will be inclined at 70° to allow forward positioning of the lower jaw. The fixed Twinblocks will be cemented onto the occlusal surfaces simply with conventional glass ionomer cement. The upper palatal arm can be expanded (prior to cementation) to allow for upper arch expansion.

Figure 1: Fixed Twinblocks with occlusal blocks adapted to the teeth and supporting wire components.

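### The primary overjet rate and the T4 date rest on ruler readings with no blinding or common measuring condition described; an arm-blind reading of the T0 and T4 models would be a cheap check

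*Protocol*

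**What the plan says.** Section 3.2.1 defines the primary outcome as "Rate of overjet correction by comparing change in millimetre/month from clinical measurements". Table 1 lists it at T0 to T5. Section 6.1 gives the method: overjet is read between the upper incisal edge and the labial surface of the lower incisors, "using a metal ruler at all appointments to assess rate of reduction". The same section uses that reading to end the Twinblock phase. T4 is reached once overjet lies within 0 to 3 mm and has not changed over two successive appointments, "for a maximum of 12 months from start of treatment".

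Section 5.5.2 has the randomisation system "generate both an on-screen message at time of randomisation and an e-mail to the PI and CI". Section 5.1 describes the local PI as the treating orthodontist. The protocol mentions no blinding of an assessor, a scan reader or an analyst.

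Section 7.1 says of the experimental appliance: "The fixed Twinblocks will be cemented onto the occlusal surfaces simply with conventional glass ionomer cement". Its blocks are inclined "to allow forward positioning of the lower jaw". The comparator in section 7.2 has the same incline but is held by clasps and can be taken out.

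The trial matrix schedules an impression or intraoral scan at T0, T4 and T5. Section 6.1 uses these for tooth movement: "The superimposition function on 3Shape Ortho Analyzer software will be used to calculate distance between pre- and post-treatment scan landmarks in millimetres". They are not assigned to overjet.

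**The concern.** One unblinded manual reading supplies the millimetres in the primary rate and also triggers the date that closes the treatment phase. A reader who expects faster correction with the fixed appliance can, without intending it, round a reading or declare T4 sooner.

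The measuring conditions may also differ by arm. At T0 nobody has an appliance in the mouth. At T1 to T3 the fixed blocks are still cemented, while the removable ones can be taken out. If a fixed-arm reading is taken with the jaw resting forward on the inclines, part of the apparent change is posture. Section 6.1 specifies the two tooth landmarks but not the jaw position or how the removable appliance is handled, so two sites could both follow it and measure different things.

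An error common to both arms would largely cancel in the comparison. An error tied to the arm would not, and no later analysis can recover a jaw position that was never recorded.

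**Working it through.** **The plan's own figure.** Section 8.1 assumes a difference of 81 days, SD 101 days, alpha 0.05 and 80% power with an independent t-test.
- Effect size: 81/101 = 0.802.
- Exact two-sided t-test: power 79.3% at 25 per arm and 80.9% at 26, so 26 per arm is reproduced.
- Dropout of 40%: 26/0.60 = 43.3, rounded up to 44 per arm and 88 in total, also reproduced.

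The sample size is not in question. The 81 days serves below only as a yardstick.

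**Inputs for scale**
- Removable arm: nine months on average (section 2), or 9 × 30.44 = 274 days.
- Fixed arm: 274 − 81 = 193 days, or 193/30.44 = 6.34 months.
- Overjet correction: assumed 5 to 8 mm.
- Reading offset in one arm: assumed 0.5 to 1 mm. The documents give no measurement error.

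**View 1: offset as a rate.** Implied planning difference = correction/6.34 − correction/9.
- 5 mm: 0.789 − 0.556 = 0.23 mm/month.
- 8 mm: 1.262 − 0.889 = 0.37 mm/month.

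Offset at six months = offset/6: 0.5/6 = 0.08 and 1/6 = 0.17 mm/month. As a share of the implied difference this runs from 0.083/0.373 = 22% to 0.167/0.233 = 72%.

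**View 2: offset as time.** Shift in T4 = offset × 193/correction.
- Smallest: 0.5 × 193/8 = 12 days, and 12/81 = 15%.
- Largest: 1 × 193/5 = 39 days, and 39/81 = 48%.

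These are two descriptions of the same error. At T4 the recorded millimetres are constrained by the 0 to 3 mm rule, so an offset there acts mainly through time. The two figures must not be summed.

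**What a shift would do to the test.** On the days scale of section 8.1, with no true effect and an assumed one-arm shift in T4, the two-sided false-positive rate at nominal 5% becomes:

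| Shift | 26 per arm | 44 per arm |
|---|---|---|
| 14 days | 7.8% | 9.9% |
| 28 days | 16.5% | 25.1% |
| 42 days | 31.3% | 48.8% |

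These are conditional figures, not predictions. The planned primary analysis is a multilevel model on mm/month, so they indicate order of magnitude only.

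**The case against.** **Who measures.** Section 6.1 names no assessor, so the treating team is an inference. It is a natural one, since readings are taken at all appointments and allocation goes to the treating orthodontist. Naming a different assessor would not by itself blind the reading, because cemented blocks are visible in the mouth.

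**Existing safeguards.** The landmarks are fixed, and T4 needs an unchanged reading at two appointments. This limits a single favourable misreading but not a systematic offset.

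**The scans.** A reader might infer that blinded, appliance-free scans are already in hand. The documents do not say so. They describe impressions or scans at T0, T4 and T5, no blinded reading, and no requirement that the T4 record follow removal of the blocks. The stated superimposition measures movement between time points, which is not an inter-arch distance. For sites that scan impressions or plaster models, no bite record is mentioned. Where a bite is captured, a blinded reader cannot undo forward posture at capture. These points stand, and the fix has to meet them.

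**Changing the primary outcome.** A reader might also conclude that a scan measure should replace the ruler rate. That is a debatable redesign. The ruler reading exists at every time point, whereas scans cover neither T1 to T3 nor the T4 trigger.

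**Bias in favour of the fixed appliance.** It is tempting to say the plan will make the fixed appliance look faster. In-appliance readings with a forward jaw would act that way, but the protocol does not say readings are taken like that. Direction is a possibility only.

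**Conclusion.** The point holds as a cheap improvement, not as a demonstrated bias. Followed as written, the protocol allows reading error that depends on the arm to enter the primary comparison, both through the millimetres and through the date of T4. It includes no arm-blind check, although it already collects dental records from which one could be made.

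The size and direction of any error cannot be found from the documents. The illustrative range (0.08 to 0.17 mm/month against 0.23 to 0.37, or 12 to 39 days against 81) rests on the assumed 0.5 to 1 mm offset, the assumed 5 to 8 mm correction, and the nine-month background figure. It shows only that an offset of that order would not be negligible beside the planning difference.

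**What to change.** Keep the clinical ruler rate as the primary outcome and amend the following.

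1. **Section 6.1, overjet.** State one measuring condition for both arms: the same jaw position, no forward posturing, and whether the removable appliance is in or out.
2. **Section 6.1, impressions and scans.** Apply the same jaw position to the bite captured with the scan. Require the T4 scan or impression to be taken after appliance removal and to include a bite record.
3. **Section 8.2.** Add a pre-stated sensitivity analysis in which the T0 to T4 overjet change is measured on coded digital models by the person already landmarking them, without the arm label.

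The cost is one added inter-arch measurement per model pair, coded file names, a bite record at sites that use impressions, and a wording amendment. It needs no extra visit, radiograph or participant, and the sample size is unchanged.

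The limit should be stated alongside it. T1 to T3 readings and the T4 trigger stay unblinded, so the check covers the millimetre change between T0 and T4 and not the T4 date. If the model-based change is divided by time to T4, that unblinded date re-enters the rate.
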